439 *within 3 weeks after randomization.*

440 **2.4 Randomization of Eligible Subjects**

441 1. Prior to randomization, the study participant's understanding of the trial, compliance with
442 device use, willingness to accept the assigned treatment group, and commitment to the follow-
443 up schedule will be reconfirmed.
444
445 2. Randomization is completed on the DRCR.net website.
446 • Study participants will be assigned randomly (stratified by site and intravitreous treatment*
447 in the non-study eye) with equal probability to one of two treatment groups:
448 ○ Active treatment (670nm wavelength) device
449 ○ Sham (broad spectrum white light) device
450

451 *Randomization will be stratified by site and recent (within 4 months) or planned intravitreous
452 treatment in the non-study eye, including intravitreous anti-VEGF and steroid
453

454 3. For participants who consent, a second randomization will determine whether the participant
455 will receive periodic text message reminders regarding device compliance.
456 • Randomization is completed on the DRCR.net website and will be stratified by assigned
457 treatment group.

458
459 Once a study participant is randomized, that participant will be counted regardless of whether the
460 assigned treatment is received. Thus, the investigator must not proceed to randomize an individual
461 until he/she is convinced that the individual is eligible and will accept whichever treatment group
462 is assigned through randomization.
463

464 **CHAPTER 3: RANDOMIZED TRIAL PROCEDURES**

465 **3.1 Study Device**

466 **3.1.1 Home Procedures**

467 While a device is assigned, the study participant will be required to use the device twice daily
468 (once in the morning and once before bed) for 90 seconds each. Participants will be provided with
469 instructions to take home for proper device use and the required timing of treatments.

470

471 **3.1.2 Primary Outcome Phase**

472 Each participant will receive the type of device for home use based on their treatment group
473 assignment (the participant will remain masked to whether the device is emitting active or sham
474 treatment):

475 ○ Active treatment (670nm wavelength) device twice a day for 90 seconds
476 ○ Sham (broad spectrum white light) device twice a day for 90 seconds

477

478 The primary outcome phase will last until completion of the '4-month' visit, which could be up to

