479 8 months post-randomization (see visit windows below). If the visit is not completed by 8 months,
480 the participant will be instructed to discontinue device use, return the study device as soon as they
481 are able, and study participation will be ended.

482

483 **3.1.3 Post-Outcome Phase**

484 At the 4-month visit, all participants will be unmasked to their treatment group assignment.

485

486 Participants originally assigned to Sham who have not already received alternative DME treatment
487 (see section 3.6) will return the original device and have the option to receive the active treatment
488 group device for the next 4 months.

489

490 Participants originally assigned to Active who have not received alternative treatment will return
491 the original device and have the option to complete the remaining follow-up visits without device
492 use.

493

494 **3.1.4 Device Training**

495 On the day of randomization, a device will be provided to the participant according to their
496 randomized assignment. In order for investigators to remain masked, clinical site coordinators
497 will instruct study participants regarding the proper use of the device. The eyelid must be closed
498 for the duration of the treatment. The participant must turn the device on and it will stop
499 automatically. The study participant will be asked to demonstrate proper use in the office, which
500 will be considered the initial treatment. The participant will be instructed to complete the second
501 treatment that day before bed.

502

503 **3.2 Study Visits and Phone Contacts**

504 A phone call is completed by site personnel within approximately one week of randomization (5
505 to 14 days) to emphasize compliance with device use and answer any questions.

506

507 Scheduled follow-up visits will occur at the following times (time from randomization unless
508 otherwise noted):

509

Visit	Target Date	Target Window (around Target Date)	Allowable Window (around Target Date)
1 Month	4 weeks	± 1 week	± 2 weeks
2 Month	8 weeks	± 1 week	± 2 weeks
3 Month	12 weeks	± 1 week	± 2 weeks
4 Month/Primary Outcome Visit*	16 weeks	± 2 weeks	-4 weeks/+16 weeks
~6 Month/2-month post outcome	8 weeks after 4- Month visit	± 2 weeks	± 4 weeks
~8 Month/4-month post outcome	16 weeks after 4- Month visit	± 2 weeks	-8 weeks/+12 weeks

510

*Key visit

511

512 The goal will be for all participants to complete all scheduled visits. However, participants who

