707 followed until it is either resolved or medically stable, even after the subject has completed all
708 applicable study visits/contacts. For all other adverse events, data collection will end at the time
709 the participant completes the study. Note: participants should continue to receive appropriate
710 medical care for an adverse event after their participation in the study ends.

711 **5.2 Reportable Device Issues**

712 All UADEs, ADEs, device complaints, and device malfunctions will be reported irrespective of
713 whether an adverse event occurred, except in the following circumstances.

714 The following device issues are anticipated and will not be reported on a Device Issue Form but
715 will be reported as an Adverse Event if the criteria for AE reporting described above are met:

- 716 • Device issues clearly addressed in the user guide manual that do not require additional
717 troubleshooting
- 718 • Brightness of light
- 719 • Mild to moderate photo blanching or color distortion immediately following use that resolves

720 **5.3 Pregnancy Reporting**

721 If pregnancy occurs, device use will be discontinued immediately and participation in the study
722 will be discontinued following the 4-month visit (or next study visit, if after 4 months). The
723 occurrence of pregnancy will be reported on an AE Form.

724 **5.4 Timing of Event Reporting**

725 SAEs and UADEs must be reported to the Coordinating Center within 24 hours via completion of
726 the online adverse event form.

727 The Coordinating Center will notify all participating investigators of any adverse event that is
728 serious, related, and unexpected. Notification will be made within 10 days after the Coordinating
729 Center becomes aware of the event.

730 Each principal investigator is responsible for reporting serious study-related adverse events and
731 abiding by any other reporting requirements specific to his/her Institutional Review Board or
732 Ethics Committee.

733 Upon receipt of a UADE report, JCHR will investigate the UADE and if indicated, report the
734 results of the investigation to the sites' IRBs, and the FDA within 10 working days of JCHR
735 becoming aware of the UADE per 21CFR 812.46(b) (2). The Medical Monitor must determine if
736 the UADE presents an unreasonable risk to participants. If so, the Medical Monitor must ensure
737 that all investigations, or parts of investigations presenting that risk, are terminated as soon as

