- 864 • Percentage of eyes with CST below OCT machine and gender-specific threshold for DME
- 865 • Percentage of eyes receiving alternative treatment for DME*
- 866 • Percentage of eyes with a 5-letter loss in visual acuity from baseline
- 867 • Mean change in visual acuity from baseline*
- 868 • Patient compliance*

869 *Outcomes marked with an asterisk will include descriptive statistics only and not statistical
 870 comparisons of treatment groups

871 To ensure that statistical outliers do not have undue impact on analyses of continuous outcomes,
 872 change in continuous outcomes from baseline will be truncated to ± 3 standard deviations based
 873 on the overall mean and standard deviation at primary outcome visit from both treatment groups
 874 combined. Analyses to be conducted on these outcomes are detailed in Section 7.8.

875 **7.5 Analysis Cohorts**

- 876 • Intention-To-Treat (ITT) Analysis Cohort: all randomized participants irrespective of
 877 treatment received, analyzed according to treatment assignment
- 878 • Safety Analysis Cohort: all randomized participants irrespective of treatment received,
 879 analyzed according to treatment assignment

880 • Per-Protocol Analysis Cohort: participants who complete primary outcome visit, 70% or
881 more of prescribed sessions of treatment, and do not receive an alternative treatment for
882 DME

883 The primary analysis will follow the intention-to-treat principle. It will include all randomized
884 participants. The data from the ITT cohort will be analyzed according to the group to which the
885 participants were assigned through randomization, regardless of treatment actually received.

886 A per-protocol analysis will be performed to provide additional information regarding the
887 magnitude of the treatment effect. The per-protocol analysis will only be performed if more than
888 10% of randomized participants would be excluded by these criteria. The intention-to-treat
889 analysis is considered primary and if the results of the per-protocol analysis and intention-to-treat
890 give inconsistent results, exploratory analyses will be performed to evaluate possible factors
891 contributing to the differences.

892 **7.6 Analysis of the Primary Efficacy Endpoint(s)**

893 The primary outcome of mean change in CST on OCT is a continuous variable. The primary
894 analysis will consist of a treatment group comparison of mean change in CST from baseline using

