948 robust variance estimation. Baseline CST and the randomization stratification factor will be
949 included as covariates.

950 The percentage of eyes receiving an alternative treatment for DME before the primary outcome
951 visit will be reported. Only participants receiving alternative treatment or completing the primary
952 outcome visit without receiving alternative treatment will be included. Statistical comparison
953 between treatment groups will not be performed.

954 The percentages of eyes with 5-or-more-letter decrease from randomization at primary outcome
955 visit is a binary variable that will be compared between treatment groups using logistic regression
956 with robust variance estimation. Baseline visual acuity and randomization stratification factor will
957 be included as covariates. The mean change in visual acuity will also be reported; however,
958 statistical comparison between treatment groups for the mean change will not be performed.

959 For each logistic regression analysis, the odds ratio for the treatment group effect, 95% confidence
960 interval, and P value will be presented.

961 **7.9 Safety Analyses**

962 All reportable adverse events will be categorized as study eye or systemic. All events will be
963 tabulated by treatment group in a listing of each reported Medical Dictionary for Regulatory
964 Activities (MedDRA) term and summarized over each MedDRA System Organ Class. All
965 randomized participants will be included in safety analyses.

966 Since there are no known risks of the device, there are no pre-specified safety outcomes of interest.
967 However, the frequency of each ocular adverse event occurring at least once per eye and each
968 systemic event occurring at least once per participant will be calculated.

969 In addition, the following will be tabulated by treatment group:

970 • For each MedDRA System Organ Class, percentage of participants with at least one
971 serious event
972 • Number of adverse events thought by investigator to be related to treatment

973 No formal statistical comparisons will be performed for reported adverse events.

974 **7.10 Outcome Measures Phase 2 (4 Months Post-Outcome)**

975 The following post-switch effects on DME from completion of the 4-month/primary outcome visit
976 to the final visit will be tabulated separately within each treatment group:

977 • Duration of effect on DME after active treatment is stopped

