7.14 Baseline Descriptive Statistics

1039 Baseline characteristics will be tabulated by treatment group and summary statistics appropriate
1040 to the distribution will be reported.
1041

1041 **7.15 Device Issues**

1042 Number of reported device issues will be tabulated by treatment group.

1043 **7.16 Planned Interim Analyses**

1044 There is no formal interim analysis planned for this study. The Data and Safety Monitory
1045 Committee (DSMC) will review tabulated safety and outcome data approximately every 6 months
1046 while the study is ongoing.

1047 **7.17 Subgroup Analyses**

1048 Subgroup analyses/assessments of effect modification (interaction) will be conducted for the
1049 primary outcome. Since there is no strong prior rationale for potential subgroup effects, these
1050 analyses will be considered exploratory and hypothesis generating, rather than definitive. It is
1051 recognized that the study is not powered to detect subgroup effects and that lack of significance is
1052 not necessarily an indication that subgroup effects do not exist. Additionally, interpretation of the
1053 analyses will depend on whether the primary analysis demonstrates a significant treatment group
1054 difference; in the absence of such a difference, subgroup analyses will be interpreted with caution.
1055 The general approach for these exploratory analyses will be to add an interaction term for the
1056 subgroup factor by treatment into the primary analysis model.

1057 Subgroup analyses will use observed data (no imputation) from participants who complete the
1058 primary outcome visit without missing CST data. Exploratory subgroup analysis will evaluate the
1059 effects of the following baseline factors:

- 1060 • Prior DME treatment: yes vs. no
- 1061 • Intravitreous treatment in non-study eye: recent (within 4 months) or planned
- 1062 • Lens status: phakic vs. pseudophakic
- 1063 • Baseline CST: continuous and categorical (dichotomized based on a clinically relevant cut
1064 point or an approximate median value)
- 1065 • Hemoglobin A1c: continuous and $<7.5\%$ vs. $\geq 7.5\%$
- 1066 • Iris color: blue, brown, or other

1067 Subgroup analyses will only be conducted if there are at least 20 eyes in each subgroup for each
1068 treatment group. There are no data to suggest that the treatment effect will vary by sex or
1069 race/ethnicity. However, both of these factors will be evaluated in exploratory subgroup analyses

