330 Adherence in Phase 2 will be evaluated only among eyes participating in Phase 2. The protocol
331 specifies that if alternative treatment is given during Phase 2, participation in the study will be
332 discontinued following next study visit. Missing data will be handled similarly to the Phase 1
333 analysis.

334 In addition, for each phase the effect of text message reminders on compliance will be evaluated
335 using the imputed dataset. Compliance will be defined as the total number of sessions of the
336 study device use during each phase divided by the total number of possible treatment sessions
337 based on visit completion status and alternative DME treatment as noted above; and only
338 participants who have been randomly assigned to receive or not receive text messages will be
339 included in this analysis. This analysis will consist of a comparison of mean compliance between

340 those receiving texts and those not receiving texts using analysis of covariance, and will include
341 treatment, number of days from randomization to the primary outcome visit for Phase 1 (and
342 number of days from the primary outcome to 4 months post outcome visit for Phase 2), and an
343 interaction between treatment group and text message reminders, given it is possible that the
344 participants who are assigned to the control group are less compliant and more likely to ignore
345 text messages. However, it is also recognized that the power for testing the interaction is low in
346 this study due to the limited sample size. If a significant interaction is not present, the analysis
347 will be conducted combining the two treatment groups. If a significant interaction between
348 treatment and text message reminders is present, a stratified analysis will be performed.

349 **5.0 Safety Analysis**

350 All reportable adverse events will be categorized as study eye or systemic. All events will be
351 tabulated by treatment group in a listing of each reported Medical Dictionary for Regulatory
352 Activities (MedDRA) term and summarized over each MedDRA System Organ Class. All
353 randomized participants will be included in safety analyses.

354 Since there are no known risks of the device, there are no pre-specified safety outcomes of
355 interest. However, the frequency of each ocular adverse event occurring at least once per eye and
356 each systemic event occurring at least once per participant will be calculated.

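### Safety and device-issue tables are by randomized group with no period limit, so Phase 2 events on active PBM fall in the sham column

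*SAP*

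**What the plan says.** **Grouping.** Protocol 7.5 defines the "Safety Analysis Cohort: all randomized participants irrespective of treatment received", "analyzed according to treatment assignment". SAP 8.1 makes randomized assignment the default for treatment comparisons.

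**Tables.** Protocol 7.9 begins: "All reportable adverse events will be categorized as study eye or systemic. All events will be" tabulated by group. SAP 5.0 repeats this, with events "tabulated by treatment group in a listing of each reported Medical Dictionary for Regulatory" Activities term. Both sections add, by group, the percentage of participants with a serious event in each System Organ Class and the number of events the investigator judged related. On device issues, Protocol 7.15 says: "Number of reported device issues will be tabulated by treatment group". SAP 6.0 lists the same item. None of these sections names a phase, a cut-off date or the device in use.

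**Collection period.** Protocol 5.1.6 follows unresolved unanticipated adverse device effects beyond the study. It then says: "For all other adverse events, data collection will end at the time" the participant completes the study. Phase 2 is therefore covered.

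**Change of exposure.** Under Protocol 3.1.3, sham participants without alternative DME treatment "will return the original device and have the option to receive the active treatment" device for 4 months. PBM participants return theirs and may stay in follow-up without one. Protocol 3.1.1 applies to any assigned device: "While a device is assigned, the study participant will be required to use the device twice daily".

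**The concern.** After the primary outcome visit the randomized label no longer describes exposure. The sham column then contains people on the active device, and the PBM column contains people on no device. A Phase 2 event that an investigator attributes to the active device would be counted under sham in the related-event table. For device issues the problem is mainly one-sided: the PBM group has returned its devices and can add few new issues, while active-device issues accumulate under sham.

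Participants are also unmasked at the 4-month visit (Protocol 3.1.3), so a pooled column mixes masked and unmasked reporting.

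The plan separates phases elsewhere. SAP Table 2 is Phase 1 only. SAP 3.0 gives Phase 2 its own outcome list and baseline table, and reports Phase 2 compliance for the initial sham group alone. Within SAP 6.0, baseline characteristics are split into overall and Phase 2 participants, but device issues are not. Neither Phase 2 outcome list (Protocol 7.10, SAP 3.0) has a safety item.

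At stake is whether the harm tables can be interpreted. Protocol 7.19 and SAP 6.0 say that a pivotal trial would follow evaluation of all the data. If the device causes an adverse effect, a table that mixes exposures can hide it.

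**Working it through.** **Inputs**

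- Planned size is 134, randomized 1:1, so 67 per arm (Protocol 7.3.2). This figure reproduces: a two-sided 5% t-test with 90% power, difference 30 and SD 50 needs 59.35, so 60 per arm or 120 in total; 120/0.9 = 133.3, giving 134. The point does not depend on it.
- Phase 1 length L1: target 16 weeks, allowable 16−4 = 12 to 16+16 = 32 (Protocol 3.2).
- Phase 2 length L2: target 16 weeks, allowable 16−8 = 8 to 16+12 = 28 (Protocol 3.2).
- Not given, so shown as ranges: u, the share of randomized sham participants who take the active device, and s, the share of PBM participants who stay in Phase 2.

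**1. Active-device time under sham**

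With equal arms and PBM participants keeping the device through Phase 1:

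share = u·L2 / (L1 + u·L2)

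At L1 = L2 = 16, the PBM column holds 67 × 16 = 1072 device-weeks. The sham column holds 268, 536 or 1072 at u = 25%, 50% or 100%. For example, 268/(1072+268) = 20%.

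| Phase lengths (weeks) | u = 25% | u = 50% | u = 100% |
|---|---|---|---|
| L1 = 32, L2 = 8 | 2/34 = 6% | 4/36 = 11% | 8/40 = 20% |
| L1 = 16, L2 = 16 | 20% | 33% | 50% |
| L1 = 12, L2 = 16 (active use stops at 16 weeks) | 4/16 = 25% | 8/20 = 40% | 16/28 = 57% |
| L1 = 12, L2 = 28 | 7/19 = 37% | 14/26 = 54% | 28/40 = 70% |

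The first and last rows put every participant at one extreme of both windows. Each totals 40 weeks, inside the 24 to 48 weeks of SAP Table 3.

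**2. Off-device time in the PBM column**

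With equal phases the share is s/(1+s): 33% at s = 50% and 50% at s = 100%.

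**3. Direction of the effect (assumed risks, illustration only)**

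The documents give no event rates. Let pa be the per-phase risk on the active device and ps the risk on sham or off device, with equal phases and no carry-over. Over the whole study:

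- PBM column: 1 − (1−pa)(1 − s·ps)
- Sham column: 1 − (1−ps)(1 − u·pa)

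With pa = 20%, ps = 5% and u = s = 50%, PBM is 1 − 0.80 × 0.975 = 22.0% and sham is 1 − 0.95 × 0.90 = 14.5%. A Phase 1 gap of 15 points becomes 7.5. At u = s = 100% both columns are 24.0% and the gap is zero.

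When u = s the gap reduces to (pa − ps)(1 − u), so a real excess on the device always shrinks. When u and s differ, it shrinks if u·pa(1−ps) exceeds s·ps(1−pa). That held in every scenario run, but it need not hold if very few sham participants switch.

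**The case against.** The strongest case is that little depends on these tables. They are descriptive, no safety outcome is pre-specified, and the trial is a pilot judged on an anatomic outcome. No test, estimate or error rate changes. Each event also receives causality assessments from the investigator and the Medical Monitor, and the DSMC reviews safety data about every 6 months. This is correct and limits the severity. The DSMC tabulations, however, are not stated to be by group or by phase, so they do not close the gap.

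A second argument is that Protocol 7.9 sits between the Phase 1 outcomes and Phase 2 (7.10), so Phase 1 may be intended, and that the reference to all events may concern type rather than time. The text allows this reading. But SAP 5.0 comes after the Phase 2 section, and a Phase 1 restriction would leave harms on the active device in Phase 2 in no planned table. A stated rule is needed under either reading.

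The figures also have limits, and these stand. Full uptake is unrealistic: the plan allows 10% loss and bars sham participants who had alternative treatment from the active device. At u = 90% with equal phases the share is 0.9/1.9 = 47%. Active use is offered for 4 months, so the 28-week row is an outer case. Exposure share is not the same as distortion in event counts.

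Finally, events could be split afterwards if onset and device-exchange dates are recorded. That may be so, but the forms are not shown and the plan does not provide for it.

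**Conclusion.** The concern holds. The absence of any period or phase limit is certain from the text. Followed literally, the assignment rule puts Phase 2 events and device issues on active PBM in the sham column and off-device time in the PBM column. If a Phase 1 restriction was intended, Phase 2 harms have no planned summary.

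The amount depends on uptake, which the documents do not give. With equal phases, 20% to 50% of active-device time sits under sham for uptake of 25% to 100%. If active use stops at 16 weeks, the highest values are 25% to 57% over the same uptake range. These figures assume equal arms and full Phase 1 device use in the PBM group. If PBM participants stop early, the share under sham rises.

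The primary analysis, Medical Monitor review and DSMC oversight are not affected. The consequence is confined to descriptive harm tables, but these are the only by-group summary of harms specified in the two documents. This should be corrected, although it does not threaten the trial's main result.

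**What to change.** State the period and the attribution rule for every safety and device-issue table.

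- **Main tables:** adverse events, serious events, related events and device issues with onset before the primary outcome visit or device exchange, by randomized group.
- **Phase 2 tables:** reported separately by original group, with sham participants split by whether they took the active device.
- **All columns:** number of participants and exposure time.

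Whole-study tables with a phase split and the device in use shown would also close the gap. What matters is that the rule is written down. Align Protocol 7.5, 7.9 and 7.15 with SAP 5.0 and 6.0.

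The cost is wording and table shells, with no new visits or tests. There will be a few more tables, and Phase 2 columns will be small because staying in the study without a device is optional. The split relies on recorded event-onset and device-exchange dates, so confirm that the forms capture both.
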